### 9.3 Clinical laboratory evaluations

Clinical laboratory hematology, chemistry and urinalysis measurements obtained from blood/urine samples collected throughout the study are presented in Table 9-1.

**Table 9-1: Laboratory measurements**

Hematology	Chemistry	Urinalysis
Basophils	ALP	Glucose
Eosinophils	ALT	pH
Hematocrit	AST	RBC
Hemoglobin	Bilirubin	Total protein
Lymphocytes	BUN or urea	WBC
MCH	Calcium	Microscopy (WBC, RBC, casts, crystals, bacteria) a
MCHC	Chloride	Other
MCV	Creatinine	FSH b
Monocytes	Glucose	
Neutrophils	HDL	
Platelet count	LDH	
RBC count	LDL	
WBC count	Magnesium	
	Potassium	
	Sodium	
	Total bilirubin	
	Total cholesterol	

ALP=alkaline phosphatase; ALT=alanine aminotransferase; AST=aspartate aminotransferase; BUN=blood urea nitrogen; FSH=Follicle Stimulating Hormone, HDL=high-density lipoprotein; LDH=lactate dehydrogenase; LDL=low-density lipoprotein; MCH=mean corpuscular hemoglobin; MCHC=mean corpuscular hemoglobin concentration; MCV=mean corpuscular volume; RBC=red blood cell; WBC=white blood cell

a Microscopy will be performed only in case of abnormalities

b Only applicable for postmenopausal women

A blood and urine sample for clinical laboratory analysis will be obtained at Entry Visit, Visit 3 up to EOS/EDV Visit. Samples are analyzed in a central laboratory. During the study, non-protocol-specified lab parameter values (unplanned) may be collected. Summaries of lab parameter values will only include those of planned visits as specified in the protocol. All lab parameter values will be listed and summarized using international units. Per-subject listings

include flag for possibly clinically significant treatment-emergent (PCST) result and calculated change from Baseline for each laboratory variable. If the subject had both scheduled sampling and unscheduled sampling at the same date/time, scheduled sample will be flagged as the analysis record. For the subjects with DILI event, lab tests are done locally for more rapid results, a concurrent sample should also be sent to the central laboratory. The central lab results will be flagged as the analysis record.

The observed value and change from Baseline will be summarized (SS) descriptively by scheduled study visit, as well as including Last Visit, maximum value, and minimal value. These summaries will also be organized by lab function panel and parameter. Data collected at unscheduled visits will not be summarized.

For hematology and blood chemistry parameters that are identified in Table 10-1, the shift from Baseline in category (relative to normal range: low, normal, high) to the maximum and minimal values during the exposure period will be presented. Categorical urinalysis results will be summarized by visit.

PCST criteria have been developed for the PSL program based on FDA Division of Neuropharmacologic Drug Products guidelines with some UCB-defined additions and are provided in Appendix 12.1. For lab parameters with treatment emergent PCST criteria, the number and percentage of subjects with a PCST will be summarized for the overall and by 3-month interval during the Exposure Period. Subject numbers for those meeting the PCST will also be presented. Results of additional tests like the urine pregnancy test will be listed.

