When PSL is stopped due to PDILI (as described in [Section 6.3.1](#)), PSL must be permanently discontinued unless a subsequent alternative diagnosis fully explains the hepatic findings. If a subsequent alternative diagnosis fully explains the hepatic findings, and the requirements provided in [Section 9.2.1.2.1](#) are met, rechallenge with PSL may be appropriate after discussion with the Sponsor.

Rechallenge with a substance potentially causing drug-induced liver injury is dangerous, may be fatal, and must not occur.

The approach to investigate PDILI is summarized in [Table 9-3](#).

Table 9-3: Required investigations and follow up for PDILI

Laboratory value			Immediate		Follow up	
ALT or AST	Total bilirubin	Symptoms ^a of hepatitis or hypersensitivity	Consultation requirements	Actions	Testing	Evaluation
≥3xULN	≥2xULN ^b	NA	Hepatology consult. ^c	Immediate, permanent PSL discontinuation.	Essential: Must have repeat liver chemistry values and additional testing completed ASAP (see Section 9.2.1.3); recommended to occur at the site with HCP.	Monitoring of liver chemistry values at least twice per week until values normalize, stabilize, or return to within Baseline values. ^d
≥8xULN	NA	Medical Monitor must be notified within 24 hours (eg, by laboratory alert) and subject discussed with Medical Monitor ASAP.	Immediate, temporary or permanent, PSL discontinuation.			
≥3xULN	NA	Yes				
≥3xULN (and ≥2x Baseline) and <5xULN	<2xULN	No	Discussion with Medical Monitor required if the criterion that allows for PSL continuation is met.	Further investigation – immediate PSL discontinuation not required (see Section 9.2.1.2).	Not required unless otherwise medically indicated (at discretion of Investigator).	
≥5xULN (and ≥2x Baseline)	<2xULN	No	Discussion with Medical Monitor required.	Immediate, permanent PSL discontinuation.	Essential: Every attempt must be made to have repeat liver chemistry values and additional testing completed within 48 hours at the site with HCP (see Section 9.2.1.3).	Monitoring of liver chemistry values at least twice per week until values normalize, stabilize, or return to within Baseline value. ^d

ALP=alkaline phosphatase; ALT=alanine aminotransferase; ASAP=as soon as possible; AST=aspartate aminotransferase; HCP=healthcare practitioner; NA=not applicable; PDILI=potential drug-induced liver injury; ULN=upper limit of normal

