### 3.2.4 Last visit during the Exposure Period

The Last Visit for an assessment is the last non-missing assessment prior to or on the date of last dose of PSL (Section 3.2.2.1). All scheduled and unscheduled will be considered. Last Visit will be determined separately for each study assessment. Last Visit during the Exposure Period will be included in the by-visit summary unless noted otherwise. Similarly, the minimum and maximum values are defined as the minimum and maximum values prior to or on the date of last dose of PSL.

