## 9.5 Vital signs, physical findings, and other observations related to safety

### 9.5.1 Vital signs

Vital measurements (including SBP, DBP, PR and RR) are taken at every scheduled visit. These measurements are generally collected in standard units. If any measurements are collected in international units, they will be converted to standard units for summaries. Subject Listings will be prepared for vitals variables including absolute change from Baseline and abnormality criteria flag.

The observed value and absolute change from Baseline will be summarized (SS) descriptively by scheduled study visit, as well as Last Visit, maximum value, and minimal value. Data collected at unscheduled visits will not be included in the by-visit summary.

The number and percentage of subjects with abnormal vital signs described in Appendix 13.2 will be summarized for the overall and by 3-month interval during the Exposure Period. Subject numbers for those meeting the abnormal criteria will also be presented.

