### 13.3 ELECTROCARDIOGRAM (ECG) – ABNORMAL

Abnormality criteria to be applied in the assessment of ECG parameter values are given below:

Parameter	Age	Abnormality Criteria
QT interval (ms)	1m-<12y	>500
	>12y	>500 or ≥60ms increase from Baseline
QTc(F) (ms)	<6m	>490, or >15% increase from Baseline
	6m-<3y	>440, or >15% increase from Baseline
	3y-<12y	>440, or >15% increase from Baseline
	>12y- <17y	>440, or >15% increase from Baseline
	≥17y	>500 or ≥60ms increase from Baseline
QTc(B) (ms)	<6m	>490, or >15% increase from Baseline
	6m-<3y	>450, or >15% increase from Baseline
	3m-<12y	>450, or >15% increase from Baseline
	>12y- <17y	>450, or >15% increase from Baseline
	≥17y	>500 or ≥60ms increase from Baseline
PR interval (ms)	<6m	>150, or >25% increase from Baseline
	6m-<3y	>170, or >25% increase from Baseline
	3y-<12y	>180, or >25% increase from Baseline
	>12y - <17y	>200, or >25% increase from Baseline
	≥17y	Treatment-emergent value >200, >220, >250
QRS interval (ms)	<6m	>90, or >25% increase from Baseline
	6m-<3y	>90, or >25% increase from Baseline
	3y-<12y	>100, or >25% increase from Baseline
	>12y - <17y	>110, or >25% increase from Baseline
	≥17y	Treatment-emergent value >100, >120, >140
Heart rate (bpm)	<6m	<100, >180
	6m-<3y	<90, >150
	3y-<12y	<60, >130
	>12y	<50, >120

Abbreviations: bpm = beats per minute; m = months; ms = milliseconds; QTc = corrected QT interval; y = years. A month is defined as 30 days; a year is defined as 365.25 days.

Note: Treatment-emergent is defined as meeting the criteria at any post-Baseline visit during EP0093 (including unscheduled visits) and not meeting the same criteria during Baseline in the parent study.

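### SAP 9.3 bars unscheduled laboratory data from summaries while SAP 3.2.4 counts them for Last Visit, maximum and minimum, so the worst-value rows and the shift table have two conflicting definitions

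*SAP*

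**What the plan says.** Two sentences in SAP 9.3 restrict laboratory summaries. One reads "Summaries of lab parameter values will only include those of planned visits as specified in the protocol". The other closes the paragraph on descriptive summaries: "Data collected at unscheduled visits will not be summarized". That same paragraph plans the rows in question, by scheduled visit and "as well as including Last Visit, maximum value, and minimal value. These summaries will also be organized by lab function panel and parameter".

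SAP 3.2.4 sets a study-wide rule. For Last Visit, "All scheduled and unscheduled will be considered". It then says that, in the same way, "the minimum and maximum values are defined as the minimum and maximum values prior to or on the date of last dose of PSL".

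SAP 9.3 goes on to plan a shift table from Baseline to the maximum and minimum during the Exposure Period, and PCST counts overall and by 3-month interval. Neither has its own rule on unscheduled samples.

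For vital signs, SAP 9.5.1 has a narrower exclusion: "Data collected at unscheduled visits will not be included in the by-visit summary".

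**The concern.** A programmer cannot follow both sections for laboratory data. Two people working correctly from this SAP could produce different Last Visit, maximum, minimum and shift results.

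The choice is not neutral. The protocol allows unscheduled visits for safety reasons at any point in the Evaluation Period (Table 5-1, footnote a) and requires abnormal hepatic tests to be repeated (9.2.1). On-treatment samples from such visits are among those most likely to hold an extreme value. Leaving them out of tables meant to show each subject's worst value would make the laboratory safety picture look cleaner than the data. Laboratory change is a listed safety variable in a study whose primary objective is long-term safety.

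**Working it through.** The documents give no figure on this point, so the check is a comparison of text followed by reasoning about direction and scale.

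**1. Does the conflict reach each output?**

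| Output | SAP 3.2.4 | SAP 9.3 as written | Result |
|---|---|---|---|
| By-visit rows | not addressed | unscheduled excluded | no conflict; 3.2.3.1 also restricts by-visit tables to scheduled visits |
| Last Visit | scheduled and unscheduled | unscheduled excluded | explicit conflict |
| Maximum, minimum | defined similarly, all values to last dose | unscheduled excluded | conflict |
| Shift to maximum/minimum | uses those extremes | uses those extremes | inherits the conflict |
| PCST counts | silent | only the general wording | ambiguous, no conflict with 3.2.4 |

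**2. Can the 9.3 sentence be read as by-visit only?** SAP 3.2.3.1 already limits by-visit tables to scheduled visits and does not map unscheduled ones to them. On that reading the 9.3 sentence would add nothing. SAP 9.5.1 shows how the narrow rule is worded when it is meant. Against this, 9.3 also says that when a scheduled and an unscheduled sample share a date and time, the scheduled one is the analysis record. That tie-break has little purpose if every unscheduled sample is barred. So 9.3 does not settle the matter even within itself.

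**3. Direction.** Let S be a subject's scheduled on-treatment values and U the unscheduled ones. Then max(S) ≤ max(S and U together), and min(S) ≥ min(S and U together). Dropping U can never add a subject whose maximum is high or whose minimum is low; it can only remove some. For example, take normal values at Months 6 and 9 and a high unscheduled on-treatment value between them. Under 3.2.4 the shift is normal to high; under 9.3 it is normal to normal. For Last Visit the direction is not fixed.

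**4. Scale.** After entry, a completer has scheduled samples at Visits 3, 4 and 5 (3), Visits 6 to 11 (6) and End of Study (1): 3 + 6 + 1 = 10. After Month 3 they are about 91 days apart. If an abnormality begins at random between visits and lasts 14 to 28 days (an assumption; the documents give no duration), a planned sample catches it with probability 14/91 = 15% to 28/91 = 31%, and misses it with probability 85% to 69%. This describes how sparse the schedule is. The loss caused by the SAP wording also depends on how many missed episodes were sampled at an unscheduled visit, and the documents give nothing on that.

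**The case against.** The strongest reply is that this is a one-line wording conflict with limited consequences. Several parts of it stand.

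- The SAP does not establish a settled blanket bar. The tie-break rule points the other way, and the planned-visits sentence directly follows one about parameters not specified in the protocol, so it may have been aimed at those. If 3.2.4 prevails, maximum, minimum and shift already include unscheduled values.
- Much of the signal survives elsewhere. Listings carry every value with a PCST flag, all potential drug-induced liver injury (PDILI) events must be reported as adverse events (Protocol 9.2.1), and potential Hy's Law has its own summary and listing (SAP 9.4), although PDILI visits that cannot be mapped are only listed. Early-discontinuation samples taken between visits go to the next scheduled visit (SAP 3.2.3.1).
- A repeat prompted by an abnormal scheduled result adds no new subject to the overall PCST count for that parameter, though it can change the maximum.
- Laboratory changes are among the other safety variables. The primary ones are treatment-emergent adverse events and those leading to withdrawal.

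Three stronger readings are tempting but unsupported.

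- A reader might infer that 69% to 85% of laboratory abnormalities would vanish from the tables. That range is the chance that a planned sample misses an episode of assumed length. An episode that nobody sampled is not removed by the SAP wording.
- A reader might point to liver follow-up, "Monitoring of liver chemistry values at least twice per week until values normalize", and count 2 × 4 = 8 lost samples in four weeks. In Protocol Table 9-3 that frequency is set against categories requiring PSL discontinuation (the extracted table may be broken). Most such samples would follow the last dose, outside the Exposure Period, and stay excluded under either reading.
- A reader might say that ECG abnormalities always count unscheduled visits. The note in SAP 13.3 does so when defining treatment-emergent, but for adults that term appears only in the PR and QRS criteria.

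**Conclusion.** The conflict between SAP 9.3 and 3.2.4 is real and in current text. It is explicit for Last Visit, follows for maximum and minimum, and passes to the shift table. If 9.3 is programmed as written, counts of high maxima and low minima can only stay the same or fall. PCST counts are undefined on this point rather than contradictory.

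The size of the undercount cannot be derived: the documents give no abnormality rate, no episode duration and no share of abnormalities found only at unscheduled visits. The undercount also arises only if 9.3 is taken to override 3.2.4. This is a specification defect in supporting safety tables, to be settled before programming. It does not affect the primary safety variables, and the values remain in the listings.

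**What to change.** In SAP 9.3, replace "Data collected at unscheduled visits will not be summarized" with the vital-signs wording, "Data collected at unscheduled visits will not be included in the by-visit summary", and add: *Last Visit, maximum, minimum, shift from Baseline and PCST counts use all scheduled and unscheduled values of protocol-specified parameters during the Exposure Period (Section 3.2.4).*

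Limit the sentence "Summaries of lab parameter values will only include those of planned visits as specified in the protocol" to by-visit rows and to parameters not specified in the protocol, so that unplanned parameters stay out of the tables as now. Keep the existing rule that central results are the analysis record; SAP 3.2.4, 9.5.1 and 13.3 give no basis for bringing in local results.

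The cost is a short wording change and one record-selection flag, with no new data collection. The downside is that reported abnormality counts may rise slightly.

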#### **9.4 Subjects with potential drug-induced liver injury (PDILI)**

There are specific criteria described in the protocol Section 9.2.1 to evaluate subjects for PDILI. The evaluations required by protocol for PDILI subjects are collected on the following CRFs:

- Most Recent Study Medication Administration, for DILI
- Laboratory Tests DILI
- Physical Examination for DILI
- Vital Signs DILI
- Hepatic Event Supplemental Medical History for DILI
- Potential Hepato-Toxic Medications Inquiry for DILI
- Symptoms of Hepatitis and Hypersensitivity for DILI
- Lifestyle DILI
- Family Medical History for DILI

PDILI is suspected if potential Hy's Law applies. In order to meet potential Hy's Law, a subject must experience the elevation in bilirubin and ALT or AST at the same visit. For example, a subject who experiences a  $\geq 2$  x ULN elevation of bilirubin at one visit and a  $\geq 3$  x ULN elevation in ALT or AST at a subsequent visit has not fulfilled the potential Hy's law criteria (see protocol section 6.3.1 and 9.1.1.3 for further details).

Potential Hy's Law is defined as:

- $AST \geq 3 \times ULN$  or  $ALT \geq 3 \times ULN$  and
- Total Bilirubin  $\geq 2 \times ULN$

A summary of number and percent of subjects meeting PDILI criteria for potential Hy's Law will be provided by visit and for any visit. Additionally, a per-subject listing for subjects with PDILI by visit for the potential Hy's law criteria relevant lab values will be provided. Further CRF information regarding DILI and PDILI will be listed. Visits due to PDILI which cannot be mapped to any study visits will only be listed.

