6.3.1 Potential drug-induced liver injury PSL discontinuation criteria

Subjects with potential drug-induced liver injury (PDILI) must be assessed to determine if PSL must be discontinued. In addition, all concomitant medications and herbal supplements that are not medically necessary should also be discontinued.

The PDILI criteria below require immediate and permanent discontinuation of PSL:

- Subjects with either of the following:
 - ALT or AST $\geq 5xULN$
 - ALT or AST $\geq 3xULN$ and coexisting total bilirubin $\geq 2xULN$

The PDILI criterion below requires immediate discontinuation of PSL:

- Subjects with ALT or AST $\geq 3xULN$ who exhibit temporally associated symptoms of hepatitis or hypersensitivity. Hepatitis symptoms include fatigue, nausea, vomiting, right upper quadrant pain or tenderness. Hypersensitivity symptoms include fever (without clear alternative cause), rash, or eosinophilia (ie, $>5\%$).

The PDILI criterion below allows for subjects to continue on PSL at the discretion of the Investigator.

- Subjects with ALT or AST $\geq 3xULN$ (and $\geq 2x$ Baseline) and $<5xULN$, total bilirubin $<2xULN$, and no eosinophilia (ie, $\leq 5\%$), with no fever, rash, or symptoms of hepatitis (eg, fatigue, nausea, vomiting, right upper quadrant pain or tenderness).

Evaluation of PDILI must be initiated immediately. It consists of the diagnostic testing and continued monitoring (specific tests dependent on laboratory results and corresponding symptoms) and consultation with a local hepatologist. The local hepatologist is the expert usually consulted by the treating physician for assessment and management of potential hepatic disease. This would usually be a hepatologist, but may be a gastroenterologist. Additional investigation and monitoring may be required and adapted based on the diagnosis after the cause of the liver injury/abnormality is confirmed.

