Evaluation of PDILI must be initiated as described in [Section 9.2.1](#). If subjects are unable to comply with the applicable monitoring schedule, PSL must be discontinued immediately. Investigators should attempt to obtain information on subjects in the case of PSL discontinuation to complete the final evaluation. Subjects with PDILI should not be withdrawn from the study until investigation and monitoring are complete. All results of these evaluations and observations, as well as the reason(s) for PSL discontinuation and subject withdrawal (if applicable), must be recorded in the source documents. The eCRF must document the primary reason for PSL discontinuation.

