8.1.7 Early Discontinuation Visit

The following procedures will be performed by all subjects discontinuing the study early:

- Verify withdrawal criteria
- Obtain TSQM-9
- Obtain C-SSRS data since the last visit
- Obtain HADS data
- Obtain QOLIE-31-P data
- Obtain SSG
- Obtain CIWA-B data
- Measure vital signs (pulse rate, systolic BP, diastolic BP, and respiratory rate), in supine position after 5 minutes of rest
- Measure body weight
- Perform brief physical examination (refer to [Section 9.3.4](#) for details)
- Perform brief neurological examination (refer to [Section 9.3.5](#) for details)
- Perform Psychiatric and Mental Status assessment
- Obtain 12-lead ECG
- Collect blood and urine samples for clinical laboratory analyses
- Perform urine pregnancy test (female subjects of childbearing potential only)
- Seizure evaluation (count and type) from subject's daily record card
- Record concomitant medication and procedures
- Record AEs
- Record health-related outcomes and HRU (refer to [Section 10.5](#) for details)
- Dispense PSL for the Taper Period
- Check PSL accountability

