9.1.1.3 Adverse events of special interest

An AE of special interest is any AE that a regulatory authority has mandated to be reported on an expedited basis, regardless of the seriousness, expectedness, or relatedness of the AE to the administration of a UCB product/compound.

Potential Hy's Law, defined as $\geq 3 \times \text{ULN}$ ALT or AST with coexisting $\geq 2 \times \text{ULN}$ total bilirubin in the absence of $\geq 2 \times \text{ULN}$ ALP, with no alternative explanation for the biochemical abnormality, must ALWAYS be reported to UCB as an AE of special interest (ie, without waiting for any additional etiologic investigations to have been concluded). Follow up information should then be reported if an alternative etiology is identified during investigation and monitoring of the subject.

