9.2.1 Evaluation of PDILI

The PDILI PSL discontinuation criteria for this study are provided in [Section 6.3.1](#), with the accompanying required follow-up investigation and monitoring detailed below. All PDILI events must be reported as an AE and reported to the study site and Sponsor within 24 hours of learning of their occurrence. Any PDILI event that meets the criterion for potential Hy’s Law must be reported as an AE of special interest (see [Section 9.1.1.3](#)), and, if applicable, also reported as an SAE (see [Section 9.1.1.2](#)).

Evaluation of PDILI consists of the diagnostic testing and continued monitoring included in [Table 9-3](#) (specific tests dependent on laboratory results and corresponding symptoms) and consultation with a local hepatologist (if applicable; discussed in [Section 9.2.1.1](#)). The local hepatologist is the expert usually consulted by the treating physician for assessment and management of potential hepatic disease. This would usually be a hepatologist, but may be a gastroenterologist. Additional investigation and monitoring may be required and adapted based on the diagnosis after the cause of the liver injury/abnormality is confirmed (details in [Section 9.2.1.4](#)).

The results of all monitoring, including laboratory testing and other testing, should be made available to the study site and Sponsor.

All initial tests resulting in abnormal hepatic laboratory values need to be repeated, but appropriate medical action must not be delayed waiting for the repeat result.

If tests are done locally for more rapid results, a concurrent sample should also be sent to the central laboratory whenever possible. Medical care decisions are to be made initially using the most rapidly available results and a conservative approach must be taken if the results from the 2 laboratory tests are significantly different. Data from the local and central laboratory are to be recorded on the applicable eCRF pages.

When PSL is discontinued, all concomitant medications and herbal supplements that are not medically necessary should also be discontinued. In these cases, the Investigator should also consider dose reduction for medically necessary concomitant medication and consider changing any medically required concomitant medication known to be hepatotoxic to a suitable alternative.

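### SAP 9.4 gives the name potential Hy's Law to a criterion without the protocol's ALP condition, and its any-visit count can leave out a joint elevation seen only on an unmapped PDILI sample

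*SAP*

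**What the plan says.** **Definition.** SAP 9.4 defines potential Hy's Law by two terms: ALT or AST at least 3xULN, and total bilirubin at least 2xULN, both at the same visit. It refers the reader to protocol 6.3.1 and 9.1.1.3, and those two sections differ.

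- Protocol 6.3.1 lists the same two-term combination, without ALP and without the name Hy's Law, under this introduction: "The PDILI criteria below require immediate and permanent discontinuation of PSL".
- Protocol 9.1.1.3 defines potential Hy's Law by the two terms plus two conditions. ALP must not be at or above 2xULN, and the case is one of raised values with low "ALP, with no alternative explanation for the biochemical abnormality, must ALWAYS be reported to UCB as an AE of special interest".
- Protocol 9.2.1 speaks of PDILI events that meet the potential Hy's Law criterion, so it treats the second as a subset of the first.

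**Count.** The number and percentage of subjects "will be provided by visit and for any visit". The same paragraph adds: "Visits due to PDILI which cannot be mapped to any study visits will only be listed". SAP 3.2.3.1 does not map unscheduled visits to scheduled ones. SAP 9.3 restricts laboratory summaries to planned visits. The one stated route back is in SAP 3.2.3.1: safety assessments at an Early Discontinuation Visit (EDV) between two scheduled visits go to the next scheduled visit. The EDV does include a laboratory draw (protocol 8.1.7: "Collect blood and urine samples for clinical laboratory analyses").

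**The concern.** The label matters because the protocol gives the name a specific meaning. Potential Hy's Law is the only AE of special interest that it names, and footnote b to Table 9-3 singles out ALP at or above 2xULN for discussion of possible biliary obstruction. A reader of the table would take its count as the protocol's potential Hy's Law count, which it is not.

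The any-visit row matters because the protocol moves the informative samples off the visit schedule. Protocol 9.2.1 states: "All initial tests resulting in abnormal hepatic laboratory values need to be repeated". Table 9-3 asks for liver chemistry at least twice per week unless another schedule is agreed, while scheduled visits are 3 months apart after Month 3. If those follow-up samples do not feed the row, a subject can meet the criterion and not be counted.

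Long-term safety is the primary objective, although laboratory changes are among the other safety variables. This is the only planned table that counts joint transaminase and bilirubin elevation.

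**Working it through.** The plan gives no figure to reproduce here, so the check compares rules and applies them to constructed subjects.

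**Step 1: the rules as logic.**
- SAP 9.4: (ALT or AST ≥3xULN) and bilirubin ≥2xULN.
- Protocol 6.3.1 criterion: the same.
- Protocol 9.1.1.3, laboratory part: the same, and not ALP ≥2xULN.

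Every subject who meets the third rule meets the first, so the SAP definition is over-inclusive and cannot lose a case. ALP is in the SAP 9.3 chemistry panel, so the extra term can be programmed. The table of changes from the protocol in SAP 3.9 does not declare the departure.

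**Step 2: constructed subjects.** Values are multiples of ULN, in the order ALT / bilirubin / ALP. They are illustrations, not data.

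| Subject | Samples | SAP row, scheduled samples only | 9.1.1.3 laboratory part, all samples |
|---|---|---|---|
| A | Day 270, scheduled: 6 / 2.5 / 1 | counted | counted |
| B | Day 270, scheduled: 4 / 3 / 3 | counted | not counted |
| C | Day 270, scheduled: 3.5 / 1.2 / 1; Day 273, unscheduled: 6 / 2.6 / 1; Day 276, unscheduled: 5 / 2.2 / 1; Day 360, scheduled: 1 / 0.8 / 1 | not counted | counted |

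Each column counts 2 of 3, yet only A is in both. The 6.3.1 criterion applied to all samples counts all 3. The two problems push in opposite directions, so the total alone shows neither.

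**Step 3: how far C depends on the reading.** C is missed only if the Day 273 and Day 276 samples are not mapped. SAP 9.4 speaks of PDILI visits that cannot be mapped, which implies that some can be, but states no rule. Visit 7 (Month 9) has a window of ±1 month in protocol 8.1.6, so a reader could place the Day 273 sample there, and C would then be counted. Under the general rule in SAP 3.2.3.1 it would not. The text does not settle which applies.

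**Step 4: does the EDV close the gap?** Only in part. Protocol 6.3.1 says: "Subjects with PDILI should not be withdrawn from the study until investigation and monitoring are complete". The EDV sample may therefore be drawn after the values have fallen. If it is drawn while both are raised, the subject is counted.

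**Step 5: do other tables cover it?** The maximum-value and PCST summaries in SAP 9.3 treat one parameter at a time and are confined to the Exposure Period, which ends at last dose. They do not count joint elevation, and they exclude samples taken after PSL is stopped. The table list in SAP 9.2 has no table for AEs of special interest.

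**Step 6: scale.** One subject in the planned 1000 or so is 1/1000 = 0.1 percentage point. No hepatic event rate is given, so the number of affected subjects cannot be estimated.

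**The case against.** **The definition is a defensible screen.** The SAP rule is inclusive, it points to both protocol sections, and the absence of an alternative explanation cannot be programmed from laboratory values. This stands as a defence of the criterion as a screen. It does not defend the name, because ALP can be programmed and the protocol uses the name for a narrower group.

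**The any-visit row may already include these samples.** It is promised separately from the by-visit rows, and the listing sentence can be read as explaining only why such visits have no by-visit row. SAP 3.2.4 also considers unscheduled assessments when defining the last visit. This stands in part: omission is one reading, not a certainty. A reader might infer that every unscheduled PDILI sample is certainly excluded, and the documents do not support that.

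**Nothing is lost from the report.** PDILI events must be reported as AEs, a per-subject PDILI listing is planned, and the PCST tables give subject numbers that allow cross-checking during exposure. This stands, and it caps the importance of the point. A reader might infer that potential Hy's Law cases disappear; they do not.

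**Local-only results should be rare.** Protocol 9.2.1 says: "a concurrent sample should also be sent to the central laboratory whenever possible". Protocol 9.2.1.3 makes the concurrent central sample mandatory for PDILI testing, and SAP 9.3 makes the central result the analysis record. This largely stands. What remains is how to treat a local result that has no central counterpart.

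**A contrast with ECGs does not help.** A reader might infer from SAP 13.3 that unscheduled visits count for ECG abnormalities in general. That note defines treatment-emergent, a term that the adult criteria use only for PR and QRS.

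**Conclusion.** The label is wrong as written: the SAP 9.4 row is a protocol 6.3.1 PDILI criterion under the name that protocol 9.1.1.3 reserves for a narrower group. This follows from the definitions and needs no assumption.

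The count problem is conditional. A joint elevation seen only on a PDILI sample that is not mapped can be left out of the any-visit row, because SAP 9.4 gives no rule for which PDILI visits are mapped. Whether it would happen depends on how the programmer reads that sentence and on when the EDV sample is drawn.

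A reader might want to state the bias as an over-count, an under-count or a percentage. The documents support none of these. The label can only add subjects, the mapping can only remove them, and neither the event rate nor the length of monitoring is given. The effect is confined to the label and count of one descriptive table. The grade is minor to should-fix.

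**What to change.** 1. **Label.** Rename the current row as ALT or AST ≥3xULN with total bilirubin ≥2xULN (protocol 6.3.1). Add a potential Hy's Law laboratory row that also requires ALP <2xULN in the same sample. Footnote that it is the laboratory part of protocol 9.1.1.3, that alternative explanations are in the listing, and how many subjects had no ALP value in that sample.
2. **Count.** State that the any-visit row uses all samples after first dose in EP0093 through final contact, including unscheduled, EDV and PDILI follow-up samples. Keep the central result as the analysis record and flag any local-only result. Leave the by-visit rows on scheduled visits with the existing EDV mapping.

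Under this rule subjects A, B and C above all enter the 6.3.1 row, and A and C enter the potential Hy's Law row.

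The cost is SAP wording, one added table row and a footnote. ALT, AST, ALP, total bilirubin and the DILI forms are already collected. The change concerns reporting only and leaves clinical management untouched.
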